**Study Title: Social and Relational Capital to Overcome Social Determinants of Health.**

**The community identified problem this project seeks to solve (380 characters):**  
**Describe Goals**

We look to implement the existing models created by The Open Table, Inc. to leverage social and relational capital and positively impact various Social Determinants of Health (SDOH) including: access to healthcare, healthcare outcomes (hospitalizations, ER visits, PCP visits), improve individual patient resilience. We further, look to positively impact burnout rates for providers that care for patients with difficult social barriers to care through enhanced community resources.

**Describe your work on the problem thus far. Outline current data and results. Describe any prior projects and, if applicable, any funding sources (2200 characters):**  
**Describe Preliminary Data**

The Open Table is an existing 501c3 that establishes support "tables" of trained volunteers and community leaders (table members) that help individuals (friends) with an identified need (housing insecurity, food insecurity, access to healthcare problems, etc.) They accomplish this through the concept of leveraging social and relationship capital to problem solve with the friend. Data from an existing project/collaboration with Anthem Blue Cross has demonstrated the following outcomes for a group of 20 mothers with substance use disorder (SUD): 156% increase in relationships, 50% reduction in hospitalizations, 64% increase in drug sobriety, 40% increase in alcohol sobriety, 67% increase in stable housing, 46% increase in food security, 60% increase in employment. This project was 18-months long and all data was collected using The Accountable Health Communities Screening Tool.

Prior to joining Mayo Clinic, the principle investigator ([name]) worked at a Federally Qualified Health Center (FQHC) as an Internal Medicine Physician at Valleywise Health. Patients in this population suffer disproportionately from healthcare disparities as a result of barriers to Social Determinants of Health (SDOH). Further, healthcare workers in this setting often experience burnout from being unable to adequately help patients through complex, multifactorial SDOH issues that negatively impact their health.

**Provide specific aims of this project (4500 characters - including spaces):**  
**Describe Aims**

The Centers for Disease Control and Prevention defines social determinants of health (SDOH) as conditions in the places where people live, learn, work, and play that affect a wide range of health and quality-of-life risks and outcomes. SDOH can be categorized into domains including healthcare access and quality, education access, economic/financial stability, neighborhood and built environment, and food security (See Figure 1; Healthy People 2030). According to the Kaiser Family Foundation, SDOH account for over a third of deaths in the US annually. Research suggests that addressing SDOH can help reduce health disparities especially among individuals from racial and ethnic minority (REM) populations (Thorton et al., 2016; Zhang et al., 2020). Despite the relationship between SDOH and healthcare outcomes, and health professionals acknowledging the utility of screening for SDOH, most clinicians do not feel confident in their ability to address SDOH and fewer routinely screen for SHoH (Schickendantz et al., 2019). There is also mixed opinions on the role of the medical workforce in addressing SDOH as some factors (e.g., housing) that are outside of the control of the healthcare system (i.e., upstream factors), however, professional societies including the American Academy of Pediatrics and the American Academy of Family Physicians recommend screening for SDOH (Davidson, McGinn, 2019). The medical team must be prepared to address SDOH if screening occurs, the lack of resources to address SDOH may prevent clinicians from screening for SDOH (Garg et al., 2016). Accordingly,

resources that can be used to address SDoH may improve compliance with SDoH screening, mitigate SDOH, and improve health outcomes, and reduce burdens placed on the medical workforce. Interventions to address SDoH are of interest to clinicians and medical systems.

This proposed study seeks to examine impact of an intervention to address SDoH among patients seeking care at a federally qualified health center (FQHC). FQHCs provide comprehensive care for medically underserved areas and populations, caring for about 30 million low-income patients annually with a higher prevalence of SDoH compared to the general population (Cole et al., 2022). The preliminary study will implement The Open Table model among patients at a local FQHC to determine whether the intervention reduces barriers to achieving optimal health outcomes (i.e., does the intervention reduce SDoH). The specific aims are listed below:

**Aim 1: Determine the feasibility of implementing The Open Table model at a FQHC.**

Hypothesis: None

**Aim 2: Examine the impact of The Open Table model on social determinants of health in a healthcare setting with specific interest in access to care, hospitalizations, and social connectedness, individual capacity-building.** We will collect pre-implementation data via structured interviews and SDoH data via the CMS Community Health Social Needs Screening tool on patients enrolled in this study to identify various metrics of SDoH including baseline number of hospitalizations and number of ER visits within the previous year, perceived social support, access to food, housing, primary care visits. We will follow patients longitudinally as we implement the Open Table model of volunteers paired with a patient to determine the impact of social and relationship capital on these outcomes. Post-intervention survey data and interviews will be collected to measure impact. Hypothesis: Social support and enhanced relationships through the Open Table model will lead to reduced SDoH.

**Aim 3: Examine the impact of enhanced community-based resources (The Open Table) on healthcare providers and social services personnel (the healthcare team) satisfaction.**

Specifically, we will be looking at the healthcare team's ability to deliver care and perceived satisfaction in caring for patients with a SDOH needs. Pre and post implementation data will be collected via the Maslach Burnout Inventory tool. We will examine structural and system-level barriers to healthcare delivery for patients with an identified SDOH need and explore the value and impact of The Open Table in these situations.

Hypothesis: Enhanced healthcare provider access to community-based resources through The Open Table model will lead to improved healthcare delivery, enhanced satisfaction and reduced burnout on the healthcare team for providers caring for patients with a SDOH need in an FQHC setting.

**Describe the planned research approach including the community engagement approach (13,500 characters):**

**Describe approach**

We will partner with a Federally Qualified Health Center (FQHC) at Valleywise health to identify and recruit patients into the study. Valleywise health is the largest safety-net healthcare organization in Arizona, serving over 430,000 ambulatory visits per year. They serve a patient population that is medically complex with challenging social barriers to healthcare including homelessness, substance abuse, food insecurity, illiteracy, etc. The healthcare team (providers and social workers) are often challenged by limited community resources to assist patient's through SDOH challenges.

We aim to recruit 30 patients (total) into this study to power the results sufficiently. These patients will have an identified SDOH need that is negatively impacting their health (as determined by the FQHC staff). Once referred, the patient will be screened with a SDOH screening tool (the CMS Accountable Health Communities Screening Tool) to establish a

baseline and interviewed to determine their individual needs, they will also complete the Brief Resilience Survey (BRS) in addition to semi-structured qualitative interviews. Screening and interviews will take place by the study coordinator and/or researchers. Once accepted into the study, the study staff will refer the participant to a member of The Open Table to implement The Open Table model (Network Table) and measure specific outcomes over the intervention period. Patient name, phone number, and email will be shared with The Open Table in order for them to contact the participants and learn more about their SDoH needs. The Network Table consists of 10 trained volunteers that will meet bi-weekly to address the patient's SDoH needs, prioritize interventions and meet with the patients as is appropriate and necessary to resolve each identified need. Once the patient's needs have been met, a seat at the table will become available and additional patients will be recruited to the table. If additional needs arise for individual patients (and there is capacity at the table) patients are welcome to rejoin the table to address additional needs throughout the 12-month study period.

We intend to implement community engagement in 2 ways. First, we will partner with a community organization/501c3 (The Open Table) to bring their model of leveraging social and relationship capital to the healthcare community. Second, we will partner with a Federally Qualified Health Center (FQHC) (Valleywise Health) to help patients with identified SDoH needs that would benefit from enhanced community-based resources. Additionally, we will partner with said FQHC to measure patient-specific impact (outcomes in relation to SDOH) and provider impact (measure impact on burnout).

Patients will be recruited to the study with the assistance of a research coordinator and in partnership with FQHC staff. This study will follow patients and providers (the healthcare team) for up to one-year post-enrollment, or until patient intervention is complete. Baseline data will be collected via structured individual patient interviews and by collecting baseline SDoH data via the CMS Accountable Health Communities Screening Tool, BRS tool. Screening data may be shared with The Open Table so they can better understand the needs of the participant. Once enrolled in the study, patients will be assigned to a Network Table of trained community volunteers that will support patients with a focus on overcoming SDoH needs to improve health. Each "table" of volunteers will be led by a project director, and each volunteer will be trained by The Open Table.

We will also recruit referring providers to the study (anticipate approximately 10 providers). These providers will be asked to complete the Maslach Burnout Index pre/post intervention.

Inclusion criteria: We will include patients that are age 18 or over with an identified SDOH need that impacts healthcare outcomes (identified by the healthcare team).

Exclusion criteria: non-english speaking patients, patients <18 years old, patients who are pregnant.

Recruitment: Potential participants with SDOH needs that are negatively impacting their healthcare will be referred by the FQHC healthcare team. Patients meeting inclusion criteria will be referred to the research team. Recruiting providers will provide eligible patients with a flyer with the research team contact information, once the flyer is returned to the research team the patient will be contacted for consideration of enrollment and consent. The research team will obtain consent for all patients appropriate for participation in the study. Providers that refer patients to the study will be asked complete a survey of baseline and post-intervention burnout (Maslach burnout inventory).

Measures:

Our primary outcomes will be responses to the following survey questions pre/post intervention: CMS Accountable Health SDOH Screening Tool and the Brief Resilience Scale (BRS).

Secondary outcome measures will include: # of hospitalizations and # of ER visits, # of primary care visits and perceived access to nutritious food, healthcare worker and/or social worker burnout evaluations (pre/post). Additionally, we will complete semi-structured qualitative interviews of each participant pre/post to determine the impact of this intervention on other aspects of their life/health.

Tertiary measures will be provider burnout scores pre and post intervention based on the Maslach Burnout Inventory.

We will obtain baseline data on # of hospitalizations in the prior 12 months, # of ER visits in the prior 12 months, # of primary care visits in the prior 12 months through patient interviews and use of the EMR. Patients will have SDoH screening via the CMS Accountable Health Communities Screening Tool at baseline. Additionally, each enrolled patient will be interviewed at baseline to understand their responses to the primary outcome measurements. To better understand the patient-specific variables that may contribute to SDoH challenges and outcomes we will also collect patient demographics (e.g., age, gender, race, ethnicity, marital status), medical information (e.g., medical comorbidities, current medications), socioeconomic status (e.g., education, income, employment), environmental data (e.g., address, census measures). Provider surveys will be collected using the Maslach Burnout Inventory.(pre and post intervention). These data will be collected via the electronic medical record, survey data from patients, and survey data from medical providers and healthcare staff.

Post-intervention we will measure patient-specific outcomes including: # of hospitalizations in the prior 12 months, # of ER visits in the prior 12 months, # of primary care visits in the prior 12 months through patient interviews and use of the EMR. Patients will have SDoH screening via the CMS Accountable Health Communities Screening Tool and the Brief Resilience Scale (BRS) after completion of the intervention. We will also collect provider survey's using the Maslach Burnout Inventory.

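### With all 30 patients on the Open Table and no comparator, the before/after tests can show change but not its cause, yet the aims and deliverables word the result as an effect; separately, the utilization windows conflict.

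*Combined protocol and SAP*

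**What the plan says.** **Design.** The Describe approach section recruits 30 patients in total. Entry rests on a need named by the clinic: "We will include patients that are age 18 or over with an identified SDOH need that impacts healthcare outcomes (identified by the healthcare team". All enrolled patients then receive the intervention: "Once enrolled in the study, patients will be assigned to a Network Table of trained community volunteers". No control, waiting-list, historical or external group is described anywhere.

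**Analysis.** Under Statistical Analysis, all quantitative patient outcomes (SDOH status, resilience, hospitalizations, ER visits, primary care visits, food access) are differences before against after in the same people. The tests are McNemar, exact McNemar, paired t or a non-parametric equivalent. The section speaks only of differences and sets no limit on how a significant one will be read.

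**Intended conclusion.** Describe Aims sets out "to determine whether the intervention reduces barriers to achieving optimal health outcomes (i.e., does the intervention reduce SDoH". Aim 2 says "Post-intervention survey data and interviews will be collected to measure impact", and its hypothesis is that the model will bring SDOH needs down. Describe Outcomes expects improvement from the project and says its data will allow use of the model in other patient groups. The same text calls the study preliminary and a proof of concept.

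**Timing.** Follow-up in Describe approach runs "for up to one-year post-enrollment, or until patient intervention is complete". A patient can finish early, since once "needs have been met, a seat at the table will become available" another patient may be recruited. The post-intervention paragraph reads "Post-intervention we will measure patient-specific outcomes including: # of hospitalizations in the prior 12 months" and places the SDOH screen and the "Brief Resilience Scale (BRS) after completion of the intervention". Statistical Analysis instead compares the twelve months before with twelve months during the intervention.

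**The concern.** A paired test asks whether the same patients differ at two times. It cannot say why. Needs can resolve unaided, through usual care or through other changes over the year, and all of these enter the same before/after difference as any Open Table effect. The limit applies to both primary outcomes and to every secondary patient count.

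SDOH status is the most exposed, because patients enter with a current need in the domain that is later re-measured, so some movement in the favourable direction is plausible without any programme.

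As worded, a significant result could be reported as impact and used to carry the model into other populations when the design cannot support that reading.

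The utilization windows are a different problem, one that a control arm would not remove: the post count is defined in ways that cannot all be true for a patient who completes before month 12.

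**Working it through.** **1. The plan's own figures.** The Bonferroni level reproduces: 0.05 / 2 = 0.025. The stated power (at least 80% at 0.05; close to or above 80% at 0.025) cannot be reproduced, because the two combinations of before/after proportions are not listed in the available text. Assuming independent before and after responses, n = 30 and two-sided exact McNemar, power at 0.05 / 0.025 is:
- 90% to 50%: 90% / 84%
- 80% to 40%: 84% / 76%
- 80% to 50%: 59% / 47%

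The statement is therefore attainable for falls of about 40 points. It concerns detection of change only and is not disputed here.

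**2. Significant change with no intervention effect, one-way.** n = 30 is from the plan. Assumed: all patients screen positive at baseline, and each resolves unaided with probability r. The documents give no value for r. If k patients resolve and none worsen, the exact two-sided McNemar p is 2 × 0.5^k:
- k = 5: 0.0625
- k = 6: 0.031
- k = 7: 0.016

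Significance therefore needs k ≥ 6 at 0.05 and k ≥ 7 at 0.025. The chance of this is P(Bin(30, r) ≥ 6) or P(Bin(30, r) ≥ 7):

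| r | alpha 0.05 | alpha 0.025 |
|---|---|---|
| 5% | 0.003 | 0.001 |
| 10% | 0.073 | 0.026 |
| 20% | 0.572 | 0.393 |
| 25% | 0.797 | 0.652 |

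**3. The same with two-way switching.** Entry depends on a need identified by the healthcare team, not on a positive screen, so some patients may screen negative at baseline and later turn positive. Assume baseline prevalence b and that each patient switches with probability s in either direction. Then P(positive to negative) = b·s and P(negative to positive) = (1 − b)·s. Chance of a significant fall, n = 30:

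| b | s = 10%: 0.05 / 0.025 | s = 20%: 0.05 / 0.025 |
|---|---|---|
| 95% | 0.053 / 0.018 | 0.432 / 0.279 |
| 90% | 0.038 / 0.012 | 0.315 / 0.192 |
| 80% | 0.018 / 0.005 | 0.151 / 0.082 |
| 70% | 0.008 / 0.002 | 0.063 / 0.030 |

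The risk runs from negligible to large according to rates that nobody has supplied.

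**4. Would a comparator fit within 30 patients?** On assumed final proportions, two-sided 0.05, 15 against 15:
- 90% v 60%: 47% power; 80% power needs 32 per arm
- 90% v 50%: 68% power; needs 20 per arm
- 80% v 40%: 62% power; needs 23 per arm

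Splitting the sample would leave it underpowered for these differences.

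**5. Utilization window.** Let the pre-enrolment rate be 1 per month, so the baseline count is 12. Take completion, and the post measurement, at month 6.
- Looking back 12 months from completion, with a true 50% fall: 6 × 1 + 6 × 0.5 = 9. The apparent fall is (12 − 9) / 12 = 25%. Six pre-enrolment months sit in both counts.
- Counting only from enrolment to completion, with no effect: 6 × 1 = 6. The apparent fall is (12 − 6) / 12 = 50%.
- Twelve months during the intervention do not exist for this patient.

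One window halves a real effect and another creates a false one.

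**The case against.** The best defence is that this is a small preliminary study with a feasibility aim, written within the character limits of an application form. Aims and hypotheses are naturally phrased as effects, the deliverables are expectations, and the analysis text itself draws no causal conclusion. Interviews of every participant before and after, analysed separately, and a broad set of covariates add context.

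Much of this stands. The single group is a reasonable choice, and no test needs to change. What does not stand is that the labels settle the matter. Proof of concept appears in the same sentence that carries the model to other populations, and no section names the missing comparator as a limitation. Interviews can illuminate how change came about but do not show what would have happened without the Open Table.

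A reader might infer several stronger things that the documents do not support:
- *That a false positive is likely.* The 57% and 80% figures rest on assumed resolution rates and on universal baseline positivity, which the entry criterion does not require.
- *That hospital and ER use peaked in the referral year.* Entry is on social need, not on utilization.
- *That the post screen is timed to the moment of resolution.* The plan says only after completion, and patients may rejoin the table if new needs arise.
- *A numerical bias for resilience.* Its analysis form is unclear: a score is listed under a difference in proportion.

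**Conclusion.** The point holds as a limit on interpretation. That there is no comparator is certain from the documents. So is the gap between a before/after analysis and aims worded as effect. The size and likelihood of bias are unknown: on assumed inputs, the chance of a significant fall with no effect ranges from under 1% to 80% at alpha 0.05, and to 65% at 0.025. It would go too far to conclude that the design is invalid or that a control arm must be added.

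The utilization window is a separate fault and is wrong as written for any patient who completes before month 12. The 25% and 50% figures assume completion and measurement at month 6 and constant rates within each period. The contradiction itself needs no assumption beyond early completion, which the follow-up wording allows.

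**What to change.** **1. Interpretation.** In Describe Aims, Aim 2, Statistical Analysis and Describe Outcomes, state that patient before/after outcomes, resilience and food access included, are reported as change from baseline with 95% confidence intervals. Add that a significant p-value will not by itself be read as impact of the Open Table or used to justify extending the model. Interview findings may be reported alongside but do not replace a comparator. This costs a few sentences and a more modest conclusion; sample size, primary tests and power statement are unchanged.

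**2. Utilization window (separate point).** Reconcile the follow-up, post-intervention and Statistical Analysis wording. Count the 12 months before enrolment against the 12 months after enrolment for every patient, whenever the table's work ends. The windows are then equal, and no post window contains pre-enrolment months. The cost is that counts must be collected to month 12 for patients who finish early, so the follow-up wording must allow it. Because counts come from interviews as well as the EMR, say how the interview part will cover the months after early completion.

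**3. Optional.** Report descriptively the months from enrolment to the post screen, and resolved and newly arising needs separately.

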#### Statistical Analysis:

Primary outcomes will be measured by:

Difference in proportion (before vs after intervention) in SDOH status and resilience score.

Secondary outcomes will be measured by:

Difference in number of hospitalizations in the 12 months before vs 12 months during intervention, difference in number of ER visits in the 12 months before vs 12 months during intervention, difference in number of primary care visits in the 12 months before vs 12 months during intervention, difference in proportion (before vs after intervention) of patients answering that they perceive they have access to nutritious food, difference in proportion (before vs after intervention) of patients answering that they perceive they have access to nutritious food.

Baseline patient demographics and clinical characteristics will be descriptively summarized. Differences in categorical endpoints before vs after the intervention will be tested using McNemar's test for paired proportions, or exact McNemar's test for small sample sizes. Differences in continuous endpoints before vs after the intervention will be tested using paired t-tests, or appropriate non-parametric test.

The semistructured interview (qualitative data) will be analyzed separately for significant impact, trend and analysis.

Provider data that are recruited for analysis of burnout will be analyzed in difference in proportion to responses pre/post on the Maslach Burnout Inventory. Given the # (10) of participants in this section, we do not expect to reach statistical significance (due to inadequate power) but we will use this as an exploratory outcome.

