#### Power Analysis:

With a sample size of 30, both combinations of before/after proportions are expected to have at least 80% power, assuming we use alpha 0.05 for testing. If we correct for multiple testing (2 primary outcomes) using a Bonferroni-adjusted alpha of 0.025, both combinations of proportion assumptions are expected to have close to or above 80% power to detect a difference before vs after intervention.

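### The plan names two primary outcomes but offers only an optional Bonferroni split; committing to Holm would hold the same 5% family error and give more power.

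*Combined protocol and SAP*

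**What the plan says.** The Measures text under Describe approach lists the primary outcomes as "CMS Accountable Health SDOH Screening Tool and the Brief Resilience Scale (BRS", each taken before and after the intervention. The Statistical Analysis section analyses both in the same way: "Difference in proportion (before vs after intervention) in SDOH status and resilience score". Neither section ranks one above the other.

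The Power Analysis section claims at least 80% power with 30 patients at alpha 0.05. It continues with "If we correct for multiple testing (2 primary outcomes) using a Bonferroni-adjusted alpha of 0.025", and says that power would then be near or over 80%. The two sets of before/after proportions behind these statements are mentioned but not given, and nor is whether the tests are one- or two-sided. The Statistical Analysis section states no multiplicity rule.

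On the place of resilience, Describe Goals includes "improve individual patient resilience". Aim 2 lists "specific interest in access to care, hospitalizations, and social connectedness, individual capacity-building", and its hypothesis is "Social support and enhanced relationships through the Open Table model will lead to reduced SDoH". The word resilience appears in no aim or hypothesis.

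**The concern.** With two primary outcomes, a reader needs to know in advance what counts as a positive result. The plan leaves two routes open, and each has a cost. Without correction, the chance of at least one false positive is well above 5%. With the Bonferroni split, each outcome is tested at 0.025 whatever happens to the other, which is stricter than 5% family control requires. In a study of 30 patients that sets its power at about 80%, power lost for no gain in error control is worth recovering. Leaving the choice open also allows it to be made after the p-values are known.

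**Working it through.** **Inputs from the plan.** Two primary outcomes; 30 paired patients; alpha 0.05, or 0.025 each if corrected.

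**Assumptions.** Two-sided tests; normal approximation; equal power for both outcomes; correlation ρ between the two test statistics of 0 or 0.5. Effects are set so that each test has 80% power, first at 0.05 and then at 0.025. Rejections in the wrong direction are neglected.

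**The plan's own figures.** 0.05 / 2 = 0.025, as stated. The stated power cannot be recomputed, because neither the proportions nor the discordance is given.

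**No correction.** Family error for two independent tests: 1 − 0.95² = 0.0975, about 9.8%.

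**Holm.** The smaller p-value is tested at 0.025. If it is significant, the other is tested at 0.05. Critical values are 2.241 and 1.960. Write A for P(Z₁ > 1.960 and Z₂ > 2.241), and B for P(both > 2.241).

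- Bonferroni: per outcome P(Z > 2.241); both outcomes B.
- Holm: per outcome P(Z > 2.241) + A − B; both outcomes 2A − B.

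**Case 1: 80% power at 0.05.** The mean of Z is 1.960 + 0.842 = 2.802, so power at 0.025 is Φ(2.802 − 2.241) = 71.2%.

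- ρ = 0: A = 0.8000 × 0.7123 = 0.5699 and B = 0.7123² = 0.5074. Holm per outcome: 0.7123 + 0.5699 − 0.5074 = 77.5%. Holm both: 2 × 0.5699 − 0.5074 = 63.2%.
- ρ = 0.5: A = 0.6244 and B = 0.5721 (bivariate normal). Holm per outcome: 0.7123 + 0.6244 − 0.5721 = 76.5%. Holm both: 2 × 0.6244 − 0.5721 = 67.7%.

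**Case 2: 80% power at 0.025.** The mean of Z is 2.241 + 0.842 = 3.083, so power at 0.05 is Φ(3.083 − 1.960) = 86.9%.

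- ρ = 0: A = 0.8693 × 0.8 = 0.6954 and B = 0.64. Holm per outcome 85.5%; both 75.1%.
- ρ = 0.5: A = 0.7328 and B = 0.6872. Holm per outcome 84.6%; both 77.8%.

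| Case | ρ | Per outcome, Bonferroni → Holm | Both, Bonferroni → Holm |
|---|---|---|---|
| 80% at 0.05 | 0 | 71.2% → 77.5% | 50.7% → 63.2% |
| 80% at 0.05 | 0.5 | 71.2% → 76.5% | 57.2% → 67.7% |
| 80% at 0.025 | 0 | 80.0% → 85.5% | 64.0% → 75.1% |
| 80% at 0.025 | 0.5 | 80.0% → 84.6% | 68.7% → 77.8% |

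**Where the gain comes from.** It comes only from the second step. The chance of at least one significant result is the same under both methods (case 1, ρ = 0: 2 × 0.7123 − 0.5074 = 91.7%). If one outcome has no real effect and the tests are independent, the other gains only about (0.8000 − 0.7123) × 0.025 = 0.2 points in case 1.

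**Fixed sequence for comparison (case 1).** SDOH first at 0.05 keeps its 80%. The BRS then needs both tests significant at 0.05: 0.80² = 64% at ρ = 0, or 69% at ρ = 0.5, against 71% under Bonferroni.

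**The case against.** A Bonferroni split over two primary outcomes is a valid design, and the plan says power stays near or over 80% after it. This is also a small single-group preliminary study with a feasibility aim, so fine-tuning alpha may look like preference. Bonferroni gives simple simultaneous confidence intervals, which Holm does not. These points stand, and they limit the weight of the finding. They do not justify leaving the rule open, and they do not alter the fact that Holm rejects whatever Bonferroni rejects.

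A reader might infer something stronger: that the BRS has no place as a primary outcome because no hypothesis names it, and that it takes half the alpha and some 7 to 9 points of power from the real question. The documents do not support this, for three reasons.

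- Resilience is a stated goal, Aim 2's reference to capacity-building is arguably related, and the Measures and Statistical Analysis sections put both outcomes on an equal footing. What remains is a gap in wording between the goals and the hypothesis.
- SDOH loses alpha only if the plan does correct.
- The size of that loss cannot be derived from the plan. With an exact McNemar test on 30 pairs and assumed improve/worsen rates, power falls from 94.8% to 90.9% at 50%/5%, from 82.3% to 74.7% at 40%/5%, and from 80.9% to 70.6% at 50%/10%. The loss therefore runs from about 4 to 10 points in these cases alone.

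**Conclusion.** The point holds as a matter of method. The plan has two primary outcomes, no committed multiplicity rule, and as its only candidate a correction that Holm improves on at the same 5% family error. On the assumptions above, the gain is about 5 to 6 points per outcome and about 9 to 12 points for showing both. It depends on both outcomes having real effects. The plan's missing proportions mean that these figures illustrate the size and do not estimate this trial's power. No shortfall in power for SDOH has been shown, and a higher rank for SDOH over resilience does not follow from the text.

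**What to change.** In the Statistical Analysis section, commit before analysis to Holm for the two primary outcomes: the smaller p-value is tested at two-sided 0.025 and, if significant, the other at 0.05. In the Power Analysis section, replace the conditional Bonferroni sentence, restate power per outcome and for both outcomes under Holm, and give the before/after proportions and discordance used. The 0.025 level stays, as Holm's first step. Holm needs one p-value per outcome, so the text should also say which single SDOH measure and which single BRS measure supply them.

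The cost is wording, plus the loss of Bonferroni's simple simultaneous intervals. If the sponsor regards SDOH as the main question, it may instead choose a fixed sequence, with SDOH first at 0.05 and then the BRS at 0.05. It should then accept that resilience cannot be claimed alone if SDOH fails. One sentence linking the BRS to Aim 2 would close the wording gap.
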